#### **5. Gore® Viabahn® Endoprosthesis (Gore)**

The Viabahn is a self-expanding stent graft. The external stent is made of Nitinol, and this is lined with a reinforced, heparin bonded ePTFE. This device is highly flexible, the most flexible of the 3 stent graft options used for branch stenting. The device will accommodate significant tortuosity within the aortic flow channel and/or the target artery. The device is less visible under fluoroscopy than is the Fluency; it has less resistance to kinking; and it does not tolerate significant size mismatch between the cuff and the target vessel. Given these issues, it is generally used a secondary option to the Fluency in the existing PS-IDE studies. The flexibility is critical in selected circumstances and as such, this device is an important addition to the overall graft construct.

#### **6. WallStent™ Endoprosthesis (Boston Scientific)**

The Wallstent is a braided self-expanding stent using an Elgiloy® material. The stent is highly flexible, kink resistant, and adapts well to changes in artery diameter and curvature. This stent is used to provide added radial force and kink resistance when deployed inside of a stent-graft, such as the Fluency, iCast, or Viabahn. The stents are longer in length and have better kink resistance, so they would be used for longer and larger branches than the Cook Zilver.

#### **7. Zenith® Distal Bifurcated Body Endovascular Stent Graft**

The Zenith Distal Bifurcated Body Endovascular Stent Graft is a bifurcated endograft designed for use as a modular component to treat the infra-renal aorta. The device is designed as a Cook Zenith Flex device however there are no supra-renal struts. This allows the device to be deployed within the branched/fenestrated device without interference with the renal branch stents. This is the same device used in the commercially available ZFEN system that is called the Zenith® Fenestrated Distal Bifurcated Body Graft, described above.

## **8. The Zenith® TX2® Endovascular Graft (Cook Medical)**

The Cook Zenith TX2 endograft is used as described above to achieve proximal and/or distal aortic fixation and seal.

## **9. Zenith Alpha™ Thoracic Endovascular Graft**

This device is used as described above to achieve proximal and/or distal aortic fixation and seal.

### **4.1.3 IMPLANTS NECESSARY FOR THE COOK t-Branch DEVICE**

The t-Branch is a standardized design of the CMD device. It uses 4 down-going cuffs. Therefore the component parts are the same as those listed in section 4.1.2 but instead of the CMD itself, the t-Branch device is used. As it uses 4 down-going cuffs, the branching stents would be either the Fluency or Gore Viabahn relined with a Wallstent or a Zilver stent.

#### Branched/Fenestrated Stent Graft

1. t-Branch Endovascular Stent-Graft
2. T-Branch Low Profile Endovascular stent graft

#### Devices used to create the branches in the patient

3. Zilver® stent (Cook Medical)
4. Fluency® Plus (Bard Peripheral Vascular) Gore Viabahn
5. Gore® Viabahn® Endoprosthesis (Gore)
6. WallStent™ Endoprosthesis (Boston Scientific)

Aortic endografts for proximal and distal extension, seal and fixation

7. Zenith® Distal Bifurcated Body Endovascular Stent Graft
8. Zenith® TX2® Endovascular Graft (Cook Medical)
9. Zenith Alpha™ Thoracic Endovascular Graft (Cook Medical)

### **1. t-Branch Endovascular Stent-Graft (Cook Medical)**

1. The t-Branch device is a single pre-fabricated version of the Thoracoabdominal Custom Branch/Fenestrated Endovascular Stent-Graft. It was designed to accommodate the visceral anatomy of a majority of patients with TAAA. It is premanufactured and can be kept available for patients who present with symptomatic TAAA requiring urgent treatment.

#### **2. t-Branch Low Profile Endovascular Stent-Graft (Cook Medical)**

Both the Cook CMD and t-Branch devices can be manufactured using the standard stainless steel Z-stents and standard woven polyester fabric, or they can be manufactured in a low profile (LP) version. The LP version uses the same materials and manufacturing process used for the Cook Alpha thoracic endograft that is currently commercially available. The Z-stents are made of Nitinol

and the fabric is a thin polyester. In either case, the same device design is used. The LP version allows for a significant reduction in delivery sheath size, down to 18F from the current 20-24F. Smaller delivery sheaths will significantly expand the eligibility for patients with TAAA, particularly women. The LP device is more costly to manufacture, and as such will be reserved for patients with small iliac artery access.

3-8: Please see Section 4.1.2 for details.

#### **REFERENCES:**

See Appendix IX for references for each of the above component parts.

The Cook Custom Thoracic Branched Endograft and the Universal Graft reference can be found in the Cook Master File on record with the FDA and are not reproduced here.

## 5.0 STUDY DESIGN

This is a feasibility prospective, consecutive enrolling, non-randomized, single institution clinical evaluation of the safety and effectiveness of physician modified thoracic endovascular grafts when used in the treatment of patients with thoraco-abdominal aortic aneurysms (TAAA).

Sixty (60) study patients will be enrolled at a single center.

### 5.1 Eligibility Criteria

#### 5.1.1 Inclusion Criteria

All patients must meet all of the following inclusion criteria to be eligible for enrollment into this study:

1. Patient is  $\geq 18$  years of age
2. Patients who are male or non-pregnant female (females of child bearing potential must have a negative pregnancy test prior to enrollment into the study)
3. Patient or Legally Authorized Representative has signed an Institutional Review Board (IRB) approved Informed Consent Form
4. Patient is considered by the treating physician and a second attending physician experienced in the care of patients with aneurysmal disease to be at high risk of open surgical repair due to one or more major medical co-morbidities (i.e. CAD, CHF, COPD, CRI, advanced age, generalized deconditioning, or other.) with ASA of 3 or more.
5. The patient has reasonable expectation of surviving the B-TEVAR procedure and has a life expectancy of greater than 1 year as determined by the PI and a second attending physician experienced in the care of patients with aneurysmal disease.
6. The patient has a thoraco-abdominal aortic aneurysm where necessary visceral branch vessels (i.e. the celiac, superior mesenteric, inferior mesenteric, renal and/or dominant spinal arteries) arise from the aneurysm or seal zones necessary for on-label thoracic endovascular repair
7. Patient has a thoraco-abdominal aortic aneurysm that meets **at least** one of the following:
  - aneurysm  $\geq 5.5$  cm in diameter
  - aneurysm has increased in size by 0.5 cm in last 6 months
  - aneurysm is believed to be causing symptoms
8. Patient has sufficient arterial access (femoral and/or iliac) that will allow delivery of the endovascular device with or without the use of a surgical conduit.
9. Patient has suitable proximal (aorta) and distal (aorta or iliac) arteries to allow for adequate fixation and seal:
  - A. Non-aneurysmal proximal aortic seal zone:
    1. with a length of 25 mm of proximal seal in non-aneurysmal aorta, with or without coverage of the left subclavian artery,

2. with an outer wall diameter of no less than 15 mm and no greater than 42 mm, and
- B. Non-aneurysmal distal aortic or iliac landing zone:
  3. With a length of at least 15 mm,
  4. Aortic seal zone no less than 15 mm and no greater than 42 mm or Iliac seal zone with an outer wall diameter of no less than 8 mm and no greater than 23 mm.
10. The patient has no more than 5 necessary visceral arteries that require flow preservation.
11. All target visceral artery seal zones are  $\geq 4$  mm in diameter.
12. Patient must be willing to comply with all required follow-up exams.

### 5.1.2 Exclusion Criteria

Patients that meet ANY of the following are **not** eligible for enrollment into the study:

1. Patient has an active systemic infection
2. Patient has a mycotic aneurysm.
3. Patient has a known hypersensitivity to contrast media that is not amenable to pre-treatment.
4. Patient has an absolute contra-indication to anticoagulation
5. Patient has known sensitivities or allergies to nitinol (nickel, titanium), polyester, polypropylene, gold, stainless steel, or solder (tin, silver)?
6. Patient has a body habitus that would inhibit adequate X-ray visualization of the aorta
7. Patient has a dominant artery to the spinal cord arising from an area of stent graft coverage that is not amenable to preservation using an endovascular branch
8. Patient is currently participating in another investigational device or drug clinical trial
9. Patient has other medical, social or psychological conditions that, in the opinion of the investigator, preclude them from receiving the pre-treatment, required treatment, and post-treatment procedures and evaluations.
10. Patient has a freely ruptured TAAA with hemodynamic instability
11. Patient has unstable angina (defined as angina with a progressive increase in symptoms, new onset at rest or nocturnal angina, or onset of prolonged angina)
12. Patient has had a major surgical or interventional procedure unrelated to the treatment of the aneurysm planned within 30 days of the TAAA repair. Adjunctive procedures for treatment of the TAAA (i.e. carotid-subclavian bypass or iliac conduit) are acceptable.
13. Patient has a history of an aortopathic connective tissue disease (e.g. Marfan or Ehlers Danlos syndromes)

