Patients will be enrolled in B-TEVAR study with a plan for 2 different pathways to treatment, either in single sitting or in a staged approach. For those patients in whom a staged approach is planned or considered, consent will be obtained and the patient enrolled prior to undergoing the TEVAR 1st stage of the procedure. These patients will be tracked with a separate follow up case report form at 1 and 12 months and annually to 5 years or until they undergo the second stage with a branched device, at which time their outcomes will be followed according to the routine case report forms. Some patients who undergo the 1st stage will not go on to have the second stage done with a branched graft. This could be due to the determination that they can indeed tolerate open repair, or due to a complex recovery after the 1st stage TEVAR. Such patients will be followed up to 5 years after enrollment. All patients who are enrolled will be followed and reported on. Patients who undergo the first stage, but not the second stage, will be reported as a sub-group of patients in the annual report.

All patients who undergo the first stage TEVAR will be treated with the same TX2 device that is in the B-TEVAR protocol. The specific peri-visceral device used for the second stage could be any one of the 5 device options, CMD, t-Branch, LP CMD or t-Branch or physician modified.

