##### **4.1.1 IMPLANTS NECESSARY FOR PHYSICIAN MODIFIED ENDOGRAFT**

A physician modified branched thoracic endograft is a commercially available, off-the-shelf endograft that has been altered at the time of the procedure by creating reinforced fenestrations in the graft through which covered stent grafts can be deployed to preserve blood flow into vital branch vessels. The graft is deployed on a sterile working table in the operating room. The locations of the fenestrations are marked on the graft according to the pre-procedure measurements. The graft fabric is cut and simultaneously heat sealed using thermal Cautery. These fenestrations/cuffs are marked with medical grade metal markers to facilitate fluoroscopic visualization during the procedure. Furthermore, the fenestrations are reinforced with a short ring of PTFE. This added material is essential as it strengthens the fenestration and creates a ring within which the branch grafts can seal. After the fenestrations have been created, marked, and reinforced, additional metal radio-opaque markers are sewn to the graft to assist in device orientation under fluoroscopy. Additional sutures may be used at that time to constrain the endograft, either in a temporary or permanent fashion to facilitate subsequent deployment. The device is re-constrained and re-sheathed within the original Zenith® TX2® delivery sheath.

The modified stent graft is then deployed to reline the peri-visceral abdominal aorta. Proximal

and distal fixation and seal can be achieved using the modified TX2® device, additional unmodified TX2® devices and/or the Zenith Alpha™ Thoracic Endovascular Graft, the Cook Zenith® Flex® or Endologix AFX™ devices depending on the aortic anatomy.

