Once the aortic stent grafts are deployed, the branches are then created. Wires and catheters are used to cross through the reinforced fenestrations into the target visceral arteries. iCast covered stents are then deployed to extend from the modified aortic graft to the target vessel. The branch stents must create a hemostatic seal with the main endograft as these branches will be constructed within the aneurysm sac. Single or multiple stents may be required for any given branch. In most cases, 1 covered stent graft is sufficient to create a suitable branch. In some cases, a second covered stent graft is required. Self-expanding bare metal stents will be required within the covered stent graft branch in selected cases for several purposes: to add outward radial strength (i.e. in the setting of intrinsic target vessel stenosis); to smooth the transition from the stiff stent graft to a tortuous target visceral artery; or to treat a downstream vessel dissection or intimal irregularity. Therefore, the mean number of stents per branch is 1 with a range of 1-3.

The following devices are considered part of the B-TEVAR physician modified investigational device:

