#### **5. Gore-Tex® CV-6 Suture (W.L. Gore & Associates, Inc)**

GORE-TEX® Suture, is a unique, microporous, nonabsorbable monofilament made of expanded polytetrafluoroethylene (ePTFE), the same material used in other GORE Medical Products including the Viabahn stent graft. The material properties of PTFE include: 1:1 needle: suture sizing to reduce needle hole bleeding and better pliability with improved fracture resistance. This suture is used to sew the reinforced fenestrations and cuffs as it has better flexibility than Prolene. This flexibility allows for balloon dilation of the branch stent grafts within the fenestration without causing fracture.

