#### **8. iCast™ stent graft (Atrium Medical)**

The iCAST™ Covered Stent is a balloon expandable endoluminal device consisting of a laser cut 316L stainless steel stent with an encapsulated cover made of expanded PTFE. The device is crimped and premounted to a multi-lumen delivery catheter. To facilitate accurate device placement, two radiopaque bands are attached to the catheter shaft marking the ends of the crimped device. This device is provided in various lengths and 5, 6, 7, 8, 9 and 10 mm diameters. The iCast stent graft can be dilated beyond their nominal diameter without fabric tears. The proximal aspect of these stents are typically “flared” with a larger non-compliant balloon at the conclusion of the procedure to maximize seal and prevent endoleak. This is the primary stent used for branch creation. It has the advantages of a small crossing profile, and it can be flared in excess of the nominal size to improve the seal at the fenestration. It has excellent conformability and stiffness. As a balloon expandable stent, it has less continuous outward radial force and is less flexible, so this stent may require re-lining with a self-expanding stent to provide those qualities in specific anatomy. [4]

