#### **4.1.2 IMPLANTS NECESSARY FOR THE COOK CUSTOM THORACIC BRANCHED DEVICE**

The commercially manufactured Cook t-Branch and thoracoabdominal custom branch/fenestrated endovascular stent-graft (CMD) utilizes the same principles as the physician modified endograft described above. The suite of Cook devices can be designed to have either reinforced fenestrations or directional short reinforced self-expanding cuffs arising from the main body of the endograft. The custom nature of the device allows for either option to be used for each target vessel. Both cuffs and fenestrations have specific anatomic advantages and disadvantages, and selection of which is used is based on each individual subjects anatomy.

Cuffs are axially oriented reinforced self-expanding extensions from the main body of the device. These cuffs are designed to be deployed above or below the target artery, so that the branch stents have a longer and less angulated course from the main body to the target. As they are longer than a fenestration, the interface between the main body and the branch stent is greater, which may result in fewer stent fractures, component separations or leaks. The distance from the target artery also allows for a greater degree of intra-operative adjustment, so that branches should tolerate minor degrees of mal-alignment without difficulty, and they may be usable even in cases of severe mal-alignment. Cuffs have the disadvantage that they require a greater degree of working room around the main body of the device. They may not be usable in the setting of a narrow aortic flow channel where there is insufficient room to maneuver the branch stent from the cuff to the target vessel. Cuffs that are caudally oriented also require brachial access to place the bridging stents. Such down-going cuffs/branches may provide improved hemodynamics for target vessels that are very down-going, such as the celiac and SMA. Branches also require greater reinforcement as they are longer and subject to greater forces along their length. Due to the increased length and mobility of branches, cuffs use self-expanding stent grafts (Fluency or Viabahn) which are often re-lined with self-expanding stents (Wallstents) to add outward radial force and stability.

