The fenestrations used in the Cook Custom Thoracic Branched Device are similar to those used in the Physician Modified device. They are radially oriented and designed to align precisely with the target vessel. Fenestrations have the advantages that they can be aligned within a small aortic flow channel, that they may provide improved hemodynamic flow for target arteries that arise perpendicularly to the axis of the aorta (most renal arteries), and they can be accessed from femoral access. Fenestrations use the iCast balloon expandable stent graft as the bridging branch stent.

The design of each endograft can be individualized to optimize these factors.

**The following devices are potential component parts of the Cook Custom Thoracic Branched graft B-TEVAR investigational device:**

Branched/Fenestrated Stent Graft

1. Thoracoabdominal Custom Branch/Fenestrated Endovascular Stent-Graft

Devices used to create the branches in the patient

2. iCast™ stent graft (Atrium Medical)
3. Zilver® stent (Cook Medical)
4. Fluency® Plus (Bard Peripheral Vascular)
5. Gore® Viabahn® Endoprosthesis (Gore)
6. WallStent™ Endoprosthesis (Boston Scientific)

Aortic endografts for proximal and distal extension, seal and fixation

7. Zenith® Distal Bifurcated Body Endovascular Stent Graft
8. Zenith® TX2® Endovascular Graft (Cook Medical)
9. Zenith Alpha™ Thoracic Endovascular Graft

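### Exclusion 5 screens for implant-material sensitivity with a closed list that omits PTFE/ePTFE, although every branched construct uses an ePTFE-covered bridging stent

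*Protocol*

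**What the plan says.** Protocol Section 5.1.2, exclusion 5, reads: "Patient has known sensitivities or allergies to nitinol (nickel, titanium), polyester, polypropylene, gold, stainless steel, or solder (tin, silver"). Nothing in it marks the materials as examples, and there is no catch-all for other components. Exclusion 9 is the only general provision that could apply. It leaves to the investigator's opinion whether some other medical, social or psychological condition rules out the required treatment, and it names no material.

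On devices, Section 2.1.4 says that the peri-visceral graft at the second stage "could be any one of the 5 device options, CMD, t-Branch, LP CMD or t-Branch or physician modified". Section 4.0 counts three options because it does not count the low-profile versions separately.

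On branch construction:
- Physician-modified graft (Section 4.1.1): "iCast covered stents are then deployed to extend from the modified aortic graft to the target vessel". The iCast has "an encapsulated cover made of expanded PTFE". The same section adds: "Furthermore, the fenestrations are reinforced with a short ring of PTFE". The suture used to sew the fenestrations and cuffs is a "nonabsorbable monofilament made of expanded polytetrafluoroethylene (ePTFE), the same material used in other GORE Medical Products including the Viabahn stent graft".
- Custom device (Section 4.1.2): "Fenestrations use the iCast balloon expandable stent graft as the bridging branch stent", whereas "cuffs use self-expanding stent grafts (Fluency or Viabahn").
- t-Branch (Section 4.1.3): Fluency or Viabahn, relined with a bare stent.
- Low-profile versions (Section 4.1.3, item 2): same design as the standard ones.

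**The concern.** The sponsor chose to handle implant-material sensitivity by naming materials in a dedicated criterion instead of leaving it to judgement. A material present in every bridged branch is missing from that list, so the criterion applied as written does not ask about it.

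What is at stake is the individual patient. The implant is meant to be permanent. Surgical conversion, as Section 8.6 defines it, means open repair with explantation, in people enrolled because open repair is high risk for them. Staged subjects are enrolled before the first-stage TEVAR, which uses no bridging stent. If a PTFE sensitivity came to light only before the second stage, the subject could be left with an incompletely treated aneurysm, a state that Section 6.1, Step 4, describes as carrying a continuing risk of rupture and death. Eligibility screening is the natural point to ask.

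**Working it through.** The plan has no figure to reproduce here. The check is a cross-reading in three steps.

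**Step 1: the cover of each bridging stent.**
- iCast: expanded PTFE (Section 4.1.1, item 8).
- Fluency: ePTFE on the inner and outer surfaces (Section 4.1.2, item 4).
- Viabahn: heparin-bonded ePTFE lining (Section 4.1.2, item 5).

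Covered bridging stents containing ePTFE: 3 of 3.

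**Step 2: the bridging stent in each device option.**

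| Option | Route | Bridging stent | ePTFE? |
|---|---|---|---|
| Physician modified | fenestration | iCast | yes |
| CMD | fenestration / cuff | iCast / Fluency or Viabahn | yes, both routes |
| t-Branch | cuff | Fluency or Viabahn | yes |
| LP CMD | as CMD | as CMD | yes, both routes |
| LP t-Branch | as t-Branch | as t-Branch | yes |

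Options in which every described route uses an ePTFE-covered stent: 5 of 5. On Section 4.0's count it is 3 of 3. In the physician-modified graft PTFE/ePTFE enters from three sources: fenestration ring, suture and stent cover. The protocol describes no PTFE-free way to build a branch.

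**Step 3: comparison with exclusion 5.** Mentions of PTFE or ePTFE in the criterion: 0.

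**Who is exposed.** Every subject who receives a branched graft. Subjects who have only the first-stage TEVAR receive no bridging stent, so 60 is an upper bound on the number exposed.

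**How many might be affected.** The documents give no prevalence of known PTFE sensitivity, so call it *p*. The expected number among the planned subjects is at most 60 × *p*, which stays below one unless *p* exceeds 1/60 = 1.7%. That the true value lies below this is an assumption; the protocol gives no figure to test it. The counts in Steps 1 and 2 show exposure and do not measure risk.

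**The case against.** The strongest reply is that nothing is misstated. The protocol never claims that exclusion 5 covers every component, and no section identifies PTFE sensitivity as a hazard. The risk lists in Section 10.0 and Appendix IX mention allergic reaction only to x-ray dye. This stands as a limit on weight: the documents do not show that the omission would harm anyone.

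The list might also be read as tracking the aortic graft platforms. TX2 is stainless steel and Dacron; the Alpha graft is nitinol, polyester, polypropylene and gold. On that reading, leaving out the branch-stent cover is a choice of scope. But the protocol states no such scope, solder is not explained by it, and Section 4.1 counts the branch stent grafts among the investigational devices.

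Exclusion 9 and the investigator's own history-taking could catch a known sensitivity. That is true, but exclusion 9 is discretionary and does not prompt the question. The component Instructions for Use might also carry a contraindication. They are listed in Appendix XI but not reproduced, so what they add cannot be judged either way.

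A reader might infer something stronger: that the list is illogical because it names merely occasional materials, nitinol and gold, while omitting a universal one. The documents do not support that. Nitinol is also in Fluency, Viabahn, Zilver and the Alpha graft, and gold markers are on Zilver and the Alpha graft, so both are in wide use. The point does not need that comparison.

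Finally, PTFE is not the only gap. Platinum/tungsten coils, bovine chromic gut, cobalt chromium (AFX), bonded heparin (Viabahn) and Elgiloy (Wallstent) are also unlisted. This stands, and it shapes the fix: adding PTFE alone would leave the list incomplete.

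**Conclusion.** The point holds as a minor patient-safety gap. Exclusion 5 is a closed list without PTFE/ePTFE, while 5 of 5 branched options place ePTFE in every bridged branch. Applied as written, it lets a subject with a known PTFE sensitivity through, with only exclusion 9 behind it.

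This rests on reading the list as closed, which its wording supports, and on the component descriptions in Sections 4.1.1 to 4.1.3. It does not rest on any estimate of how common or how harmful PTFE sensitivity is. It would be going too far to conclude that such a patient has no route to exclusion, or that subjects are known to be at risk; the protocol shows neither. No sample-size, endpoint or analysis figure is touched.

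**What to change.** In exclusion 5, after the existing materials, add: PTFE/ePTFE, or any other component of the devices to be implanted. Make the same change on the Inclusion/Exclusion Worksheet. The open wording also covers the other unlisted materials, so the list need not be revised whenever a component is added.

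This is a cheap improvement: one phrase in two places. The downside is very few, if any, additional exclusions among patients at high risk for open repair. Each would matter to that patient, since Section 2.1.1 cites a series in which 55% of untreated patients had died by a median of 12 months. The protocol already accepts that trade-off for known sensitivity to the materials it lists.
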